##### **B Test Phase**

###### **1. Enrollment period**

The enrollment period begins with the pre-test visit and ends with the 3rd test visit. The enrollment period will be limited to 3 months to decrease intra-subject variability. Throughout the study, energy balance and stable metabolic control are important because of their influence on insulin sensitivity,

hypoglycemia sensing, and hunger. Participants will therefore be asked to continue on their normal, weight-maintaining diet, exercise regimen and insulin plan. Participants will be instructed to wear a continuous glucose monitor or check blood glucose at a minimum of 6 times a day for 72 hours prior to each study visit to ascertain absence of hypoglycemia and near-normal BG control. Participants are advised to check blood or urine ketones according to their usually prescribed regimen. Customary reasons to check for ketones include hyperglycemia > 250 mg/dl, illness or preceding insulin omission or insulin pump failure. Subjects may check blood or urine ketones with their usual test strips. Participants will be instructed to call the study personnel and reschedule their visit if:

- they are ill
- they have symptomatic hypoglycemia below 50 mg/dl within 24 hours of the visit
- they have ketosis (blood ketones >0.6 or urine ketones >trace) in the setting of hyperglycemia or insulin omission within 24 hours of the visit
- they have hyperglycemia above 250 mg/dl the morning of the visit

## 2. Study Visits

At all visits, participants will present in the AM after a 10-12-h overnight fast to BIDMC CRC to standardize for circadian metabolic and hormonal fluctuations. Participants will be weighed and insulin pump and glucometer or continuous glucose monitoring data (if available) will be downloaded to evaluate energy balance and metabolic control at the beginning of each visit. In the CRC, an iv catheter will be inserted into an antecubital vein for the administration of insulin. Point of care glucose will be obtained and analyzed immediately. The visit will be rescheduled if blood glucose is below 50 or above 250 mg/dl. A second catheter will be inserted into a distal forearm or hand vein for the withdrawal of blood samples. A hotbox will be used to warm the hand to arterialize the venous blood. While in the MRI scanner, the hotbox will be replaced by a heated gel pack. Insulin pump will be discontinued and iv insulin infusion will be given for 5 ½ hours at each of the four visits. At each visit, participants will consume a test-meal at baseline and an ad-libitum, standard weighed meal at the end of the visit.

### 2.1. Pre-test visit

The study director or PI will meet participants at the BIDMC GCRC, confirm eligibility and obtain informed consent. Participants will receive a low GI meal with optimal iv insulin coverage using a negative feedback algorithm to maintain euglycemia (euglycemic clamp), as outlined in 3.3.1.. Insulin requirement will be quantified. At some time during the visit, participants will be transferred to the BIDMC imaging facility for a 5-minute practice MRI session, during which they will be positioned in the scanner and undergo a brief imaging sequence to get accustomed to the scanning process and eliminate anxiety as a confounder of imaging data. Insulin infusion may be briefly discontinued while in the MRI scanner.

### 2.2. Test visits

In a double-blinded cross-over design, three test visits will serve to evaluate brain function, metabolic, and hormonal parameters. Sessions will be at least 1 week apart to eliminate habituation to the scanning process and carry-over effects, but no more than 4 weeks apart to limit intra-subject variability. At each test visit at the BIDMC GCRC and imaging facility, one of the following experimental conditions will be applied in a randomized, blinded cross-over design: (a) high GI meal with euglycemic clamp, (b) low GI meal with euglycemic clamp, (c) high GI meal with primed-variable insulin infusion at the rate established during the pre-test visit. As the high GI meal is associated with higher insulin requirement, this condition will result in moderate hyperglycemia. Thus, the design will allow comparison between a high and low GI meal with matched blood glucose but different insulin levels (condition a vs. b) **or** matched insulin with different blood glucose levels (condition b vs. c) (figure 1). After steady state insulin infusion is achieved, baseline laboratory studies will be obtained and participants will be transferred to the BIDMC imaging facility for their baseline scan. Postprandial imaging times are chosen to study cerebral blood flow and functional connectivity between brain areas of interest at the peak of blood glucose and insulin requirement (+1 h) and at the nadir of blood glucose/ insulin (+4 h). Because compensatory mechanisms and potential overeating are expected in

the late postprandial period, this will be the main focus of the study. As most prior studies on intake regulation focus on the early postprandial phase, that time point will place the research in the context of the current literature. Test meals (3.1.) will be administered directly after the baseline imaging and participants will remain in the imaging facility through their 1-hour postprandial scan, and then transferred back to the GCRC. They will remain in the GCRC until the time of their 4-hr scan, for which they will be transferred to the imaging facility and then come back to the GCRC for the ad libitum weighed meal (3.2.) (see figure 2 for locations of respective procedures). Between imaging, participants will be allowed to engage in a quiet activity such as reading. Insulin infusion and glucose monitoring will be continued in the MRI scanner. For this purpose, the study physician and a CRC nurse will accompany the participant to the MRI suite and remain there for ~ 90 minutes for the first scanning period and 30 minutes for the second scanning period. In addition to frequent point of care blood glucose sampling, arterialized blood samples will be collected from an indwelling catheter at baseline and every 30 minutes for 4 hours. Samples will be processed and stored at -80 degrees Celsius for further analyses of pertinent metabolic and hormonal parameters including plasma glucose, insulin, C-peptide, FFA, ghrelin, GLP-1, PYY, CCK, glucagon, and leptin. To correlate brain activation with behavioral endpoints hunger will be assessed every 30 minutes on a 10-cm visual analog scale ranging from “not at all hungry” to “extremely hungry”. At the end of each visit, we will quantify ad libitum food intake of a standardized weighed meal.

### 3. Interventions

#### 3.1. Test meals:

LOW GI	HIGH GI
Food	Food
Cornstarch	Corn syrup
Fructose	Fructose
Vanilla extract	Vanilla extract
Milk, 1% fat	Milk, 1% fat (+ lactase)
Egg white, dried	Egg white, dried
Olive oil	Olive oil

**Table 2.** Composition of test-meals

After baseline assessments, we will initiate timed consumption of a liquid test meal over 5 minutes, to facilitate conjunction with the MRI session. High and low GI test meals have been previously developed by our group, ingredients are listed in Table 2. The meals have similar macronutrient composition (60% carbohydrate, 15% protein, 25% fat), micronutrient profiles, physical properties, palatability and sweetness. Meals will provide 25% of individual daily energy requirements as estimated by the Harris Benedict equation. The high vs low GI

meals have a predicted difference in GI of 90 vs 40. Consistent with this prediction, a pilot study in obese young adults found a 2.2-fold difference in glycemic response ( $p < 0.001$ ). This was confirmed in our previous study in healthy obese men (15).

#### 3.2. Weighed ad libitum meals:

[figure not shown]
At the screening visit participants will select a meal according to their food preferences. The test meal will be prepared at CRC metabolic kitchen according to the following macronutrients breakdown: 60% carbohydrate, 15% protein, 25% fat. The meal will be large enough that it cannot be finished (~1000-1500 kcal), and served in multiple servings (e.g. quarters of a sandwich). Participants will be instructed to eat as much as they would like to satiate their hunger. Participants will self-administer insulin according to their usually prescribed regimen. The meal will be weighed before and after consumption and caloric intake and macronutrient composition will be calculated. The same meal will be used at each study visit.

#### 3.3. Insulin administration

##### 3.3.1. Euglycemic clamp - pre-test visit, experimental conditions a & b (figure 1)

During the entire clamp protocol, glucose levels will be measured every 5 minutes. A basal insulin infusion will be started at 80% of the patients insulin pump basal rate, and will be adjusted between 0.1 and 2.5 mU/kg·min, depending upon the patient’s plasma glucose level in relation to the target range target of 90-100 mg/dl according to a negative feedback mechanism. Once steady state is achieved, baseline laboratory studies and imaging will be obtained and test meal administered. Based on our preliminary study using the same test meals in 12 non-diabetic overweight and obese males (15), we anticipate a steep increment in insulin requirement within the first 30 minutes postprandial.

Figure 1: Anticipated serum insulin levels

Serum insulin peaked at 30 minutes postprandial and increment in plasma insulin was on average 110 µU/ml after the high GI meal and 55 µU/ml after the low GI meal.

We will therefore implement a stepwise increase in insulin infusion rate within the first 30 minutes after the test meal. Increments are informed by our previous experience wherein each increment in the insulin infusion rate of 0.1 mU/kg·min raises the circulating insulin concentration by 6 µU/ml, as well as participants' individual insulin per carbohydrate ratios. We will aim to maintain postprandial blood glucose levels within a target range of 70-140 mg/dl.

#### 3.3.1.1. High GI meal (condition a)

After consumption of the test meal, insulin infusion rate will be increased by 0.2-0.3 mU/kg/min every five minutes until blood glucose starts to fall, with further adjustments based on blood glucose trajectory. We then anticipate a stepwise decrease in insulin infusion rate, reaching basal rates at 2-3 hours postprandial. Blood glucose sampling and insulin infusion will be continued according to a negative-feedback mechanism for 4 1/2 hours postprandial. Then, insulin infusion will be discontinued and insulin pump therapy resumed according to the participants' home regimen using their own equipment.

#### 3.3.1.2. Low GI meal (screening visit and condition b)

After consumption of the test meal, insulin infusion rate will be increased by 0.1-0.2 mU/kg/min every five minutes until blood glucose starts to fall, with further adjustments based on blood glucose trajectory. We then anticipate a stepwise decrease in insulin infusion rate, reaching basal rates at 3 hours postprandial. Blood glucose sampling and insulin infusion will be continued according to a negative-feedback mechanism. for 4 1/2 hours postprandial. Then insulin infusion will be discontinued and insulin pump therapy resumed according to the participants' home regimen using their own equipment.

#### **Insulin administration chart**

Planned insulin infusion rates to account for meals are depicted. Rates may vary based on individual insulin requirements and measured blood glucose as outlined above.

Time (minute)	Insulin infusion rate (mU/kg/min)	
	HGI	LGI
pre-meal	0.2	0.2
5	0.5	0.3
10	0.8	0.5
15	1.1	0.6
20	1.4	0.8
25	1.2	0.8
30	1.1	0.7
35	1.0	0.7
40	0.8	0.7
50	0.8	0.6
70	0.8	0.4
100	0.7	0.5
130	0.5	0.4
160	0.3	0.4
200	0.2	0.3
220-end	0.2	0.2

Example: Based on this chart, the total meal insulin administered for an 80 kg male would be 8 units for the high GI and 5 units for the low GI meal. These are customary amounts of mealtime insulin.

Due to individual differences in insulin requirement, actual administered rates of insulin will vary between 0.1 and 2.5 mU/kg·min. For patient safety, rates outside this specified range may be necessary at times.

**3.3.2. Primed-variable insulin infusion - experimental condition c (figure 1)**

In the run-in period, glucose levels will be measured every 5 minutes. A basal insulin infusion will be initially administered at 80% of the patients insulin pump basal rate, and will be adjusted between 0.1 and 2.5 mU/kg·min, depending upon the patient’s plasma glucose level in relation to the target range target of 90-100 mg/dl. Once steady state is achieved, baseline laboratory studies and imaging will be obtained and test meal administered. Then, a primed-variable infusion of insulin will be administered at the rate established during the pre-test visit to achieve similar plasma insulin levels. For patient safety, glucose levels will be measured every 30 minutes. If glucose levels are > 400 mg/dl or < 60 mg/dl, insulin infusion will be adjusted to maintain glucose levels target of 60-400 mg/dl. Insulin infusion will continue for 4 1/2 hours postprandial. Then, Insulin infusion will be discontinued and insulin pump therapy resumed according to the participants’ home regimen using their own equipment.

[figure not shown]

Figure 1:

**Figure 1: Schematic depiction of anticipated glycemic changes and insulin levels during the different experimental conditions.** Theoretical glycemic response to the meal is plotted in gray, anticipated insulin requirements in blue and resulting blood glucose in green. (a) High GI meal with euglycemic clamp, (b) low GI meal with euglycemic clamp, (c) high GI meal with primed-variable insulin infusion at the rate established during the pre-test visit. As the high GI meal is associated with higher insulin requirement, this condition will result in moderate hyperglycemia. Thus, the design will allow comparison between a high and low GI meal with matched blood glucose but different insulin levels (experiment 1 - condition a vs. b) **or** matched insulin with different blood glucose levels (experiment 2 - condition b vs. c)

## 4. Assessments

### 4.1. Data to confirm eligibility

#### 4.1.1. Pre-enrollment medical record review (if patient recruited from participating institution)

- Age
- Sex
- Insulin pump use
- Date of initial Diagnosis
- Total daily insulin dose
- Current Hemoglobin A1C (within 3 months)
- Weight (within 3 months and within 1 year), height
- Medical problems
- Medications
- Allergies / dietary restrictions
- Time of last episode of DKA
- Occurrence of hypoglycemia (BG <50 mg/dl)

#### 4.1.2. At initial telephone screening

- **Elicit if medical record unavailable:** age, sex, date of initial diagnosis, weight (within 3 months and within 1 year), height, current Hemoglobin A1C (within 3 months). Participant will be asked to provide written confirmation of HbA1C (e.g. recent clinic note or laboratory printout).
- **Confirm (or obtain if medical record unavailable):** last episode of DKA, occurrence of hypoglycemia (BG <50 mg/dl), insulin pump use, total daily insulin dose, medical problems,

medications, allergies / dietary restrictions.

- **Elicit always:** Current complaints, smoking or illicit substance abuse, levels of physical activity, current weight loss diet, willing and able to: maintain weight and document for duration of the study, MRI exclusion criteria (according to BIDMC MRI checklist).

**4.1.3. At the pre-test visit**

- Height via double-measurement using a wall-mounted stadiometer.

**4.1.4. At each visit**

- Hemoglobin A1C
- Weight wearing a hospital gown or minimal clothing and socks without shoes via double-measurement using an electronic scale
- Insulin pump and glucometer or continuous glucose monitoring data will be downloaded and reviewed.

**4.2. Safety measures**

[figure not shown]
- Vital signs and blood pressure will be determined at the beginning and end of each visit from the left arm using an automated system (Dinamap, Criticon Inc, Tampa, FL). The cuff will be sized appropriately for the diameter of the arm.
- Point of Care hemoglobin will be checked once at the beginning of the study to ascertain subjects are not anemic (Hemoglobin cut-off 12.5 mg/dl).

**4.3. Process measures**

[figure not shown]
- Fasting C-peptide via CLIA certified methods at the pre-test visit.
- Point of care blood glucose will be checked every 5 minutes during the pre-test visit and conditions a and b. Glucose checks will be spaced out to every 30 minutes after administration of the test meal during condition c.

**4.4. Study outcomes**

Figure 2:

Test visits - conditons (a) and (b)

**Figure 2: Schematic depiction of study visit flow.** A – pre-test visit, B – study visit a and b. C – study visit c. Upper row: hash marks represent point of care glucose monitoring; arrows represent venous blood sampling. Blood glucose will be measured every 5 minutes during the clamp design and every 30 minutes during primed-variable insulin infusion. Middle-row: black boxes represent timed MRI scans, open boxes represent practice MRI session and MPRAGE sequence (time variable). Bottom row: Arrow represents test meal, box represents ad-libitum weighed meal, gray bar represents iv insulin infusion. Location of intervention is encoded: white background – GCRC; grey background- imaging facility.

#### 4.4.1. Imaging

All imaging will be performed without contrast on the 3T scanner at the BIDMC research imaging facility (East Campus, Ansin 3). Participants will be asked to change into hospital gowns, to minimize the potential of unseen objects within pockets and metallic attachments to clothing. Participants will be instructed to lay still and rest with closed eyes during the image acquisition. They will then be positioned in a GE HD/X (GE Healthcare, Milwaukee, WI) in supine position. An imaging coil will be placed around their head. Participants will be given earplugs to minimize noise from the scanner and a squeeze ball that triggers an alarm to indicate a desire to exit. Participants will also be able to communicate by an intercom system to the operator. All scans will be performed by an experienced radiologic technologist.

Participants will undergo a 3 plane localizer, ASL and rs-fMRI scan at baseline, 1 hour and 4 hours postprandial. Between the baseline and 1-hour scan, an MPRAGE dataset will be obtained for anatomical correlation.

#### 4.4.2. Laboratory Analyses

Arterialized venous blood samples will be collected at baseline and then every 30 minutes over a 4 1/2 hour period postprandially (figure 2). Blood volume will not exceed 140 ml per study visit or 420 ml over the study period. Samples will be processed and frozen at -80 degree Celsius for later batched analyses. We will use the following or comparable kits for sample analysis: plasma glucose, APEC Glucose Analyzer (APEC, Inc, Peabody, MA); serum insulin, Abbott IMx (Abbott Laboratories, Abbott Park, IL); serum fatty acids, Hitachi 917 Analyzer (Wako Chemicals USA, Inc, Richmond, VA). Plasma ghrelin, GLP-1, PYY, CCK, glucagon, and leptin will be analyzed as part of the metabolic

hormone panel (Luminex xMAP (Milliplex, Millipore, MA). To eliminate blood waste we will use a closed phlebotomy system (VAMP, Edwards Lifesciences Corp., Irving, CA).

#### 4.4.3. Metabolic profiles

Samples will be obtained at baseline, 1 hour and 4 hours postprandial to be analyzed by the Metabolomics Core at Broad Institute. This Core has developed an LC-MS/MS methodology that uses several chromatographic stationary phases and analyzes > 400 sugars, sugar phosphates, nucleotides, amino acids, organic acids, and lipids (e.g. individual cholesterol esters, triglycerides, diacylglycerols, phospholipids, and lysophospholipids) in a targeted manner. The platform is designed on the principle that a metabolite can be identified by its parent ion mass (MS) and dominant product ion mass (MS/MS) on a sensitive mass spectrometer in combination with its retention time on an appropriate chromatography column. While none of these three parameters is individually sufficient to uniquely identify a metabolite in a biological fluid, the three in combination provide a “tag” that marks the metabolite to permit identification and quantification.

#### 4.4.4. Psychophysics

Hunger will be assessed every 30 minutes throughout the session. We will ask participants, “How hungry are you right now?” To obtain a response to this question, we will use a 10-cm visual analog scale ranging from “not at all hungry” to “extremely hungry”, consistent with methods used in our preliminary studies (15). Participants will be instructed to put a single vertical hash mark on the scale when responding.

### **5. Randomization**

In this crossover trial, 3 conditions will be administered in 2 different sequences. As statistical comparison will only be made between condition (a) and (b), and (b) and (c), never between (a) and (c), the 2 orders will be (a)->(b)->(c), or (c)->(b)->(a). Condition b will always be adjacent to one of its comparators, limiting intra-subject variability, and the order of the compared conditions will be random. A randomization list of intervention sequences will be generated by the Clinical Research Program (CRP) at Boston Children’s Hospital.

The study director will be supplied with a numbered log for assignment of sequential randomization numbers (RID) as participants are enrolled. This log will only contain the RID.

The randomization log will be given to the BIDMC GCRC nutrition core and not shown to any study staff. It will contain the RID, sequence of conditions and a letter-code for each condition, in which only condition b is identifiable (e.g. B, X and Y).

Participants are randomized the day before the first test-visit, after participation is confirmed by phone. As each participant is enrolled, the study director will enter the participant’s unique study ID into the log, next to the next open RID. The study director will then communicate this information to the BIDMC GCRC nutrition core. The BIDMC GCRC nutrition core will reveal the experimental condition to the study physician to allow assignment to the appropriate insulin paradigm. Meals will be prepared accordingly and are labeled with the RID only and no information on the experimental condition.

For data pre-processing, the date of the MRI images will be obscured to maintain the blind. Only the letter code (e.g. B, X and Y) for each condition will be revealed to allow for single-subject and group analyses of brain response. After completion of all statistical analyses, the study director will be unblinded to the nature of the dietary intervention. If a participant withdraws before supplying usable data, the subject’s RID will not be reused or assigned to another enrollee. If a participant withdraws after one test-visit, available data will be analyzed but not included in the group analysis. If a participant withdraws after two test-visits, available data will allow for full analysis of one experiment and will be included in the group analysis. The randomization list will be slightly longer than needed in order to allow for such extra entries.

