### **B1. PURPOSE OF PROTOCOL**

**Objective:** To disentangle the postprandial effects of blood glucose and insulin on brain activation in relation to a high glycemic index (GI) meal.

Patients with type 1 diabetes mellitus (T1DM) have elevated rates of dysregulated eating and obesity (1,2). We hypothesize that these phenomena are exacerbated by effects of insulin and downstream metabolites on brain areas involved in food craving; specifically the Nucleus Accumbens (NAcc). If true, high GI meals might trigger craving and overeating, as this diet is associated with higher insulin requirements. We will dissect the role of insulin vs. glucose in mediating brain activation in response to a high GI meal by applying high vs. low GI meals with optimal (euglycemic clamp) vs. matched (primed-variable infusion) insulin coverage.

**Aim 1: To examine the effects of insulin - in relation to a high GI meal - on brain activation and food intake in the early and late postprandial period.**

Hypotheses:

1. (Primary) In the late postprandial period (4 hrs postprandial), blood flow to the NAcc will be greater after a high vs low GI meal when differences in glycemia are prevented by insulin.
2. In the late postprandial period, functional connectivity of the NAcc and prefrontal and limbic areas of intake control will be higher after a high vs low GI meal when preventing differences in glycemia.
3. Subjective food craving and ad libitum food intake will be associated with NAcc blood flow and prefrontal-NAcc functional connectivity in the late postprandial period.
4. In the early postprandial period (1 hr postprandial), blood flow will be decreased in the hypothalamus in response to a high vs. low GI meal.

**Aim 2: To examine the effects of glucose - in relation to a high GI meal - on brain activation and food intake in the early and late postprandial period.**

Hypotheses:

5. In the late postprandial period, NAcc activation will not differ between the high and low GI meal when insulin exposure is matched, in spite of the resulting hyperglycemia.
6. In the late postprandial period, functional connectivity of the NAcc and prefrontal and limbic areas of intake control will be similar after a high vs low GI meal.
7. In the early postprandial period, hypothalamus blood flow will be lower after the high vs. low GI meal.

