#### 2.5. SIGNIFICANCE

We aim to disentangle the effects of variations in blood glucose and insulin on brain function in the postprandial state among youth with T1DM. The outcome of this work would have not only scientific but also clinical implications. If NAcc activation and its likely adverse effects are mediated by glucose excursion, optimal insulin coverage should be sufficient to prevent this problem. If it is mediated by insulin or its downstream effects, however, a high GI diet might trigger craving and overeating despite optimal insulin coverage. Thus, our findings will point the way to a heightened focus on improved insulin delivery to optimally control blood glucose *versus* measures to decrease insulin demand, including a low GI diet.

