## B. Statistical Considerations

### **Sample Size Justification and Analysis Plan**

[name], a biostatistician based in the CHB Clinical Research Program and affiliated with the Endocrinology Division, collaborated with us on the power calculations and statistical analysis plan.

Multiple testing. Although Aims 1 and 2 cover several hypotheses and measures, one endpoint is primary: blood flow in the NAcc at 4 hr after feeding. Our power analysis thus primarily focuses on two comparisons, embodied in Hypothesis 1 (Aim 1) and Hypothesis 5 (Aim 2). The remaining hypotheses concern secondary outcomes. We would not consider changing the sample size for the sake of detecting effects in these outcomes and have therefore not pursued power analyses for them. We will of course conduct rigorous statistical analysis on the secondary outcome variables and deduce whatever we can from the available data, but our resource planning is aimed above all at the question of 4-hr postprandial blood flow in the NAcc.

Power analysis. We view the design, illustrated in Fig. 1, as a crossover study with two experimental conditions (A: high GI, high insulin, normal glucose; C: high GI, low insulin, high glucose) and a common comparison condition (B: low GI, low insulin, normal glucose).

Our original analytic plan (alternative #1) calls for two pre-specified comparisons (A vs B and C vs B), conducted as if they were independent experiments, using 5% type I error for each comparison without adjustment for multiple testing. The assumption of independence may seem questionable because of the correlation among each subject's three observed outcomes —  $A + \delta + \epsilon_1$ ,  $B + \delta + \epsilon_2$ , and  $C + \delta + \epsilon_3$  under a random-effects or compound symmetry assumption, where A, B, and C are fixed means for the three conditions and  $\delta$  and  $\epsilon_i$  are independent Gaussian deviates — but this assumption is justified by the fact that the crossover analysis will hinge on two within-subject contrasts that are statistically independent:

$$\text{Cov}((A + \delta + \epsilon_1) - (B + \delta + \epsilon_2), (C + \delta + \epsilon_3) - (B + \delta + \epsilon_2)) = 0.$$

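### The plan has no direct test that the insulin effect (a versus b) differs from the glucose effect (c versus b), because it bars the a versus c comparison

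*Combined protocol and SAP*

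**What the plan says.** Section B1 states the aim: "We will dissect the role of insulin vs. glucose in mediating brain activation in response to a high GI meal". It does so by combining the meals with "optimal (euglycemic clamp) vs. matched (primed-variable infusion) insulin coverage". The power analysis labels the two experimental conditions "A: high GI, high insulin, normal glucose; C: high GI, low insulin, high glucose" and the common comparator "B: low GI, low insulin, normal glucose". So a and c share the high GI meal, and b is the only low GI condition.

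Section 2.2 (Test visits) and the Figure 1 legend give each planned comparison its role. One has "matched blood glucose but different insulin levels (condition a vs. b"). The other, b versus c, has insulin matched and glucose different.

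Section 5 (Randomization) uses the restriction to these two pairs to justify the sequences abc and cba: "As statistical comparison will only be made between condition (a) and (b), and (b) and (c), never between (a) and (c"). The Statistical Considerations settle on alternative #1, two pre-specified paired comparisons, each at an unadjusted 5%. Under Data Analyses, Hypotheses 1 and 5 are both tested by paired t-test, controlling for baseline and meal order. Hypothesis 5 predicts no difference, and no equivalence margin is given for it.

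**The concern.** Hypothesis 1 predicts that a exceeds b, and Hypothesis 5 predicts that c does not differ from b. If the results come out that way, the natural reading is that insulin, and not glucose, raises NAcc blood flow. That reading compares two effects, but the plan never compares them. One result below 0.05 and another above it, against the same comparator, can easily arise when the two effects are equal or when one is half the other.

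At stake is the attribution across the two hypotheses, which is what section 2.5 (Significance) draws on when it weighs better insulin delivery against lower insulin demand. The primary test, Hypothesis 1, is not affected.

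**Working it through.** **Inputs.** From the Sample Size Justification: n = 15; SD(D) = 30 units (20 in the prior study); two-sided α = 0.05; mean flow 548 units; prior effect 7.9%, that is 0.079 × 548 = 43.3 units. The model is condition mean + subject effect + independent error, with the same SD(D) for every pair, so SD(error) = 30/√2 = 21.2.

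**1. The plan's own figure.** (2.1448 + 0.868) × 30/√15 = 23.3 units, and 23.3/548 = 4.3%. At 90% power: (2.1448 + 1.345) × 30/√15 = 27.0 units = 4.9%. Both reproduce.

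**2. The missing contrast.** (a−b) − (c−b) = a−c. Under the model a−c has the same SD as a−b, so its detectable difference is also 23.3 units at 80% power. Its 95% CI half-width is 2.1448 × 30/√15 = 16.6 units (3.0% of 548), or 11.1 units at SD 20.

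**3. How often the pattern misleads.** Simulation under this model used paired t-tests on 14 df, at least 100,000 trials per scenario, and no baseline or order covariates. The two planned contrasts share the error of b, so they correlate at 0.5 in the simulation. The pattern is a−b significant and positive with c−b not significant.

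| True effect a, c versus b (units) | SD(D) | Pattern appears |
|---|---|---|
| 15, 15 | 30 | 17% |
| 20, 20 | 30 | 16% |
| 23.3, 23.3 | 30 | 12% |
| 23.3, 23.3 | 20 | 1% |
| 43.3, 43.3 | 30 | below 0.1% |
| 23.3, 11.65 | 30 | 53% |
| 23.3, 0 | 30 | 76% |

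The first five rows have equal true effects. A direct a−c test rejects there at its nominal rate of about 5% two-sided. When the pattern appears under equal effects of 15 to 23.3 units at SD 30, a−c is significantly positive in only about 11% of those trials.

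**4. Cost of requiring a−c as well.** With effects of 23.3 and 0 at SD 30, a−b and a−c each have 80% power. The probability that both are significant and positive is 68%, against 76% for the pattern alone. With effects of 23.3 and 11.65 it is 27%.

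**5. Period balance.** In sequence abc, a−c carries the visit effects p1 − p3; in cba it carries p3 − p1. These cancel with equal allocation. With 15 participants split 8:7 the residue is (8 − 7)(p1 − p3)/15 = (p1 − p3)/15, unless order is adjusted for, as Data Analyses plans.

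**The case against.** The two planned comparisons are deliberate and each has a clear meaning. One matches glucose and the other matches insulin, and Hypotheses 1 and 5 test what they state. The meals are designed to be similar in macronutrients, micronutrients, physical properties, palatability and sweetness, so using different meals in each comparison is the exposure of interest and not an oversight. The sponsor also considered a three-condition closed test with pairwise comparisons before choosing alternative #1. All of this stands.

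A reader might infer that the objective has no test at all, or that a versus c is the comparison that answers section 2.5. The documents do not support either. Section 2.5 says that, if glucose is the mediator, "optimal insulin coverage should be sufficient to prevent this problem". Whether activation persists under optimal coverage is tested by a versus b. Nor does a−c isolate insulin: between a and c, insulin and glucose move in opposite directions. A null a−c could mean equal effects, a meal effect or no effect.

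It is also true that no section states in words that insulin will be declared the driver if one test is significant and the other is not. The risk is in how the pair of results would be read, and the plan offers no other basis for comparing them.

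Finally, the risk under equal effects is small if the prior study's SD or effect size recurs. But that study was in overweight and obese participants without diabetes, and this trial is sized on SD 30 and 23.3 units.

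**Conclusion.** The point holds as a gap in the inference across Hypotheses 1 and 5. It is not a fault in either test. The plan has no direct test that the two effects differ, and a contrast in significance cannot stand in for one.

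With equal true effects and SD 30, the misleading pattern occurs in roughly 12% to 17% of trials between 15 and 23.3 units. It becomes negligible at the prior study's effect size. With c at half of a's 23.3-unit effect, it occurs in about half of trials although c has a real effect.

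These figures assume the plan's equal-variance model, 15 completers, and no gain or loss from the baseline and order adjustment.

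**What to change.** In section 5 (Randomization), delete the statement that a and c are never compared. The two sequences can stay, since b remains adjacent to each planned comparator. Keep Hypotheses 1 and 5 as they are.

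Pre-specify the within-subject a−c difference in 4-hour NAcc blood flow with its 95% CI, adjusted for baseline and order like the other paired tests, as a supplementary test read after Hypothesis 1. State that any claim that the insulin effect exceeds the glucose effect rests on a−c and not on one test being significant and the other not. Describe a−c as a same-meal contrast in which insulin and glucose move in opposite directions, so that it complements the planned contrasts and does not replace them.

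The cost is protocol wording and one more contrast on data already collected. The drawbacks should be stated:

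- Joint power for a−b and a−c is about 68% (23.3 versus 0 units, SD 30).
- a and c are two visits apart, which is 2 to 8 weeks under the 1-to-4-week spacing, so SD(a−c) may exceed 30.
- Only completers contribute. A participant who leaves after two test visits supplies a−b or c−b, never a−c.
- Period balance is exact only with a 1:1 split or with order adjustment.
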